1288 the baseline score, and the difference divided by the baseline score, expressed in units
1289 of percent. The mean percentage change is derived as the least squares mean for
1290 treatment/visit interaction from the mixed model shown in 4) below.

- 1291 2) M-N Method:

1292 The M-N method will be used for the primary efficacy analysis, which provides
1293 point estimates for the difference between treatments, and their corresponding

1294 [REDACTED]

1296

1302

1311
1312
1313
1314
1315

1324
1325

1332

[REDACTED]

An unstructured (UN) covariance matrix will be used to fit each MMRM model. If the model does not converge using an unstructured covariance matrix, other covariance structures will be tested.

[REDACTED]

[REDACTED]

[redacted] [redacted]

[redacted] [redacted]

[redacted]	[redacted]	[redacted]
[redacted]	[redacted]	[redacted]
[redacted]	[redacted]	[redacted]
[redacted]	[redacted]	[redacted]
[redacted]	[redacted]	[redacted]
[redacted]	[redacted]	[redacted]
[redacted]	[redacted]	[redacted]
[redacted]	[redacted]	[redacted]
[redacted]	[redacted]	[redacted]
[redacted]	[redacted]	[redacted]
[redacted]	[redacted]	[redacted]
[redacted]	[redacted]	[redacted]
[redacted]	[redacted]	[redacted]
[redacted]	[redacted]	[redacted]
[redacted]	[redacted]	[redacted]
[redacted]	[redacted]	[redacted]
[redacted]	[redacted]	[redacted]
[redacted]	[redacted]	[redacted]
[redacted]	[redacted]	[redacted]
[redacted]	[redacted]	[redacted]

[redacted] [redacted]

[redacted]	[redacted]	[redacted]
[redacted]	[redacted]	[redacted]
[redacted]	[redacted]	[redacted]
[redacted]	[redacted]	[redacted]
[redacted]	[redacted]	[redacted]
[redacted]	[redacted]	[redacted]

[Redacted]	[Redacted]	[Redacted]
[Redacted]	[Redacted]	[Redacted]
[Redacted]	[Redacted]	[Redacted]
[Redacted]	[Redacted]	[Redacted]
[Redacted]	[Redacted]	[Redacted]
[Redacted]	[Redacted]	[Redacted]
[Redacted]	[Redacted]	[Redacted]
[Redacted]	[Redacted]	[Redacted]
[Redacted]	[Redacted]	[Redacted]
[Redacted]	[Redacted]	[Redacted]
[Redacted]	[Redacted]	[Redacted]
[Redacted]	[Redacted]	[Redacted]
[Redacted]	[Redacted]	[Redacted]
[Redacted]	[Redacted]	[Redacted]
[Redacted]	[Redacted]	[Redacted]
[Redacted]	[Redacted]	[Redacted]
[Redacted]	[Redacted]	[Redacted]
[Redacted]	[Redacted]	[Redacted]
[Redacted]	[Redacted]	[Redacted]
[Redacted]	[Redacted]	[Redacted]
[Redacted]	[Redacted]	[Redacted]
[Redacted]	[Redacted]	[Redacted]

[REDACTED]	[REDACTED]	[REDACTED]
[REDACTED]	[REDACTED]	[REDACTED]
[REDACTED]	[REDACTED]	[REDACTED]
[REDACTED]	[REDACTED]	[REDACTED]
[REDACTED]	[REDACTED]	[REDACTED]
[REDACTED]	[REDACTED]	[REDACTED]
[REDACTED]	[REDACTED]	[REDACTED]
[REDACTED]	[REDACTED]	[REDACTED]
[REDACTED]	[REDACTED]	[REDACTED]
[REDACTED]	[REDACTED]	[REDACTED]
[REDACTED]	[REDACTED]	[REDACTED]
[REDACTED]	[REDACTED]	[REDACTED]
[REDACTED]	[REDACTED]	[REDACTED]
[REDACTED]	[REDACTED]	[REDACTED]
[REDACTED]	[REDACTED]	[REDACTED]
[REDACTED]	[REDACTED]	[REDACTED]
[REDACTED]	[REDACTED]	[REDACTED]
[REDACTED]	[REDACTED]	[REDACTED]
[REDACTED]	[REDACTED]	[REDACTED]
[REDACTED]	[REDACTED]	[REDACTED]
[REDACTED]	[REDACTED]	[REDACTED]
[REDACTED]	[REDACTED]	[REDACTED]
[REDACTED]	[REDACTED]	[REDACTED]
[REDACTED]	[REDACTED]	[REDACTED]
[REDACTED]	[REDACTED]	[REDACTED]
[REDACTED]	[REDACTED]	[REDACTED]
[REDACTED]	[REDACTED]	[REDACTED]
[REDACTED]	[REDACTED]	[REDACTED]

[REDACTED]	[REDACTED]	[REDACTED]
[REDACTED]	[REDACTED]	[REDACTED]
[REDACTED]	[REDACTED]	[REDACTED]
[REDACTED]	[REDACTED]	[REDACTED]
[REDACTED]	[REDACTED]	[REDACTED]

[REDACTED]

[REDACTED]	[REDACTED]	[REDACTED]
[REDACTED]	[REDACTED]	[REDACTED]
[REDACTED]	[REDACTED]	[REDACTED]
[REDACTED]	[REDACTED]	[REDACTED]
[REDACTED]	[REDACTED]	[REDACTED]
[REDACTED]	[REDACTED]	[REDACTED]
[REDACTED]	[REDACTED]	[REDACTED]
[REDACTED]	[REDACTED]	[REDACTED]
[REDACTED]	[REDACTED]	[REDACTED]
[REDACTED]	[REDACTED]	[REDACTED]
[REDACTED]	[REDACTED]	[REDACTED]
[REDACTED]	[REDACTED]	[REDACTED]
[REDACTED]	[REDACTED]	[REDACTED]
[REDACTED]	[REDACTED]	[REDACTED]

[REDACTED]	[REDACTED]	[REDACTED]
[REDACTED]	[REDACTED]	[REDACTED]
[REDACTED]	[REDACTED]	[REDACTED]
[REDACTED]	[REDACTED]	[REDACTED]
[REDACTED]	[REDACTED]	[REDACTED]
[REDACTED]	[REDACTED]	[REDACTED]
[REDACTED]	[REDACTED]	[REDACTED]
[REDACTED]	[REDACTED]	[REDACTED]
[REDACTED]	[REDACTED]	[REDACTED]
[REDACTED]	[REDACTED]	[REDACTED]
[REDACTED]	[REDACTED]	[REDACTED]
[REDACTED]	[REDACTED]	[REDACTED]
[REDACTED]	[REDACTED]	[REDACTED]
[REDACTED]	[REDACTED]	[REDACTED]
[REDACTED]	[REDACTED]	[REDACTED]
[REDACTED]	[REDACTED]	[REDACTED]
[REDACTED]	[REDACTED]	[REDACTED]
[REDACTED]	[REDACTED]	[REDACTED]
[REDACTED]	[REDACTED]	[REDACTED]
[REDACTED]	[REDACTED]	[REDACTED]
[REDACTED]	[REDACTED]	[REDACTED]
[REDACTED]	[REDACTED]	[REDACTED]

[REDACTED]	[REDACTED]	[REDACTED]
[REDACTED]	[REDACTED]	[REDACTED]
[REDACTED]	[REDACTED]	[REDACTED]
[REDACTED]	[REDACTED]	[REDACTED]
[REDACTED]	[REDACTED]	[REDACTED]
[REDACTED]	[REDACTED]	[REDACTED]
[REDACTED]	[REDACTED]	[REDACTED]
[REDACTED]	[REDACTED]	[REDACTED]
[REDACTED]	[REDACTED]	[REDACTED]
[REDACTED]	[REDACTED]	[REDACTED]
[REDACTED]	[REDACTED]	[REDACTED]
[REDACTED]	[REDACTED]	[REDACTED]
[REDACTED]	[REDACTED]	[REDACTED]
[REDACTED]	[REDACTED]	[REDACTED]
[REDACTED]	[REDACTED]	[REDACTED]
[REDACTED]	[REDACTED]	[REDACTED]
[REDACTED]	[REDACTED]	[REDACTED]
[REDACTED]	[REDACTED]	[REDACTED]
[REDACTED]	[REDACTED]	[REDACTED]
[REDACTED]	[REDACTED]	[REDACTED]
[REDACTED]	[REDACTED]	[REDACTED]
[REDACTED]	[REDACTED]	[REDACTED]
[REDACTED]	[REDACTED]	[REDACTED]
[REDACTED]	[REDACTED]	[REDACTED]
[REDACTED]	[REDACTED]	[REDACTED]
[REDACTED]	[REDACTED]	[REDACTED]

1340 **APPENDIX 1 PASI SCORING**

1341 PASI is evaluated within each of the four body regions: a) head, b) upper limbs, c) trunk, and
1342 d) lower limbs;

- 1343 [redacted]
[redacted]
- [redacted] [redacted]
[redacted]
 - [redacted] [redacted]
[redacted]
 - [redacted] [redacted]
[redacted]
 - [redacted] [redacted]
[redacted]
 - [redacted] [redacted]
[redacted]
 - [redacted] [redacted]
[redacted]
 - [redacted] [redacted]
[redacted]
 - [redacted] [redacted]
[redacted]
 - [redacted] [redacted]
[redacted]
 - [redacted] [redacted]
[redacted]
 - [redacted] [redacted]
[redacted]
 - [redacted] [redacted]
[redacted]
 - [redacted] [redacted]
[redacted]
 - [redacted] [redacted]
[redacted]
 - [redacted] [redacted]
[redacted]
 - [redacted] [redacted]
[redacted]
 - [redacted] [redacted]
[redacted]
 - [redacted] [redacted]
[redacted]

1366 **APPENDIX 2 DLQI SCORING**

1367 The Dermatology Life Quality Index (DLQI) questionnaire is an assessment of treatment
1368 response on the subject's quality of life to measure how much the scalp psoriasis has affected
1369 the subject's life during the previous week. [REDACTED]

[REDACTED]

[REDACTED]

[REDACTED]

[figure not shown]
[REDACTED]

[figure not shown]
[REDACTED]

[REDACTED]

[REDACTED]

[REDACTED]

[REDACTED]

[REDACTED]

[REDACTED]

[REDACTED]

[REDACTED]

[REDACTED]

[REDACTED]	[REDACTED]
------------	------------

[REDACTED]	[REDACTED]
------------	------------

[REDACTED]	[REDACTED]
------------	------------

[REDACTED]	[REDACTED]
------------	------------

[REDACTED]	[REDACTED]
------------	------------

[REDACTED]

• [REDACTED]
[REDACTED]
[REDACTED]
[REDACTED]

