Safety assessments including adverse event (AE)/serious adverse event (SAE) monitoring, vital signs, physical examinations, electrocardiogram, and laboratory measurements will be performed during the study.

[REDACTED]

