- 238 • To assess the effect of tildrakizumab on IGA (scalp only), Scalp Itch NRS, PASI,
239 PGA-S (whole body), and IGA mod 2011 (whole body), at week 12 and other
240 measured time points through Week 52.
- 241 • To assess the time to response
- 242 • To assess the efficacy of tildrakizumab in the improvement of scalp itch as measured
243 by the proportion of subjects achieving a 4-point reduction in Scalp Itch Numeric
244 Rating Scale (NRS) score from Baseline at Week 16 compared with placebo
- 245 • To assess the efficacy of tildrakizumab in the treatment of moderate to severe
246 psoriasis (entire body including scalp) compared with placebo as measured by
247 Psoriasis Area and Severity Index (PASI), IGA mod 2011 (whole body), Physician
248 Global Assessment for skin (PGA-S) score (whole body), and total body surface area
249 (BSA) involvement at Week 16.

250 **2.3 Exploratory Objective**

251 The exploratory objective of this study is:

- 252 • To assess the effect of tildrakizumab on Quality of Life measured by: Dermatology
253 Life Quality Index (DLQI).

254 **3 OVERALL STUDY DESIGN AND TREATMENT PLAN**

255 The overall study design and treatment plan are described in Sections 4.1 of Clinical Protocol
256 TILD-18-20 [REDACTED]. A brief overview is included below.

257 This is a multicenter, randomized, double-blind, placebo-controlled Phase 3 study to assess
258 the efficacy and safety of tildrakizumab in the treatment of moderate to severe psoriasis of
259 the scalp. The study will enroll approximately 214 subjects with moderate to severe psoriasis

260 of the scalp. Eligible subjects will be randomized to 1 of the 2 arms [REDACTED] Arm A:
261 Tildrakizumab 100 mg, subcutaneous (SC) (n=107) and Arm B: Placebo, SC (n=107).

262 The study will comprise 3 parts:

263 **PART 1: Double-blind Placebo-controlled (Day 1 to Week 16)**

264 After a Screening Period of up to 28 days and on Day 1, all eligible subjects will be
265 randomized 1:1 to receive either tildrakizumab 100 mg or placebo administered by SC
266 injection [REDACTED]. Subjects should receive the first dose of study
267 treatment within 24 hours of randomization. The treatment period for the double-blind
268 placebo-controlled part of the study is 16 weeks. All assessments of efficacy and safety
269 before or on the date of injection at Week 16 [REDACTED]
[REDACTED] are considered in PART 1.)

271 **PART 2: Double-blind Active Treatment Extension (Week 16 to Week 52)**

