272 At Week 16, subjects initially randomized to placebo will be switched over to receive
273 tildrakizumab 100 mg [REDACTED] while subjects initially randomized to
274 tildrakizumab 100 mg will continue to receive tildrakizumab [REDACTED]. In
275 order to maintain the blind, subjects who were initially randomized to placebo will receive
276 matching placebo injections [REDACTED] while subjects who were initially
277 randomized to tildrakizumab will receive matching placebo injections at Weeks 20, 32, and
278 44. All assessments of efficacy and safety after the date of injection at Week 16 and before or
279 on the date of injection at Week 52 [REDACTED] [REDACTED] are
280 considered in PART 2.

281 **PART 3: Observational Safety Follow-up (Week 52 to Week 72)**

282 After Week 52 [REDACTED] the study treatment
283 should be stopped and all subjects, including those who terminated early from Part 1 and 2
284 will enter [REDACTED] Observational Safety Follow-up Period to monitor safety and
285 tolerability [REDACTED] following last dose of study treatment. During the follow-up period,
286 subjects should continue on study-approved concomitant medications only, however may be
287 placed on appropriate therapies for safety concerns or significant worsening of psoriasis
288 based on the judgment of the Investigator. The subjects will not receive study treatment
289 during the follow-up period. [REDACTED]
[REDACTED]

292 4 STATISTICAL CONSIDERATIONS OF PROTOCOL

293 4.1 General Statistical Consideration

294 All summaries and analyses conducted will be by assigned therapy and/or combined total
295 subjects. Data obtained on the eCRF and entered into the database will be provided in data
296 listings showing individual subject values.

297 Descriptive statistics (number [n], mean, standard deviation [SD], median, first quartile [Q1],
298 third quartile [Q3], minimum [min], and maximum [max]) for continuous variables and
299 frequency distributions and percentages for discrete variables will be utilized. Categorical
300 variables will be summarized by frequencies and percentages.

301

306 All tabulations of summary statistics, graphical presentations, and statistical analyses will be
307 performed using SAS® Version 9.4 or higher.

308 4.1.1 Baseline and Study Day

309 For purpose of the SAP, Day 1 is defined as the date of first administration of study drug.
310 Study day is calculated relative to the date of Day 1.

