[redacted] placebo-controlled treatment without any major protocol deviation that could impact
393 data interpretability for the primary efficacy endpoint. [redacted]
[redacted]

- [redacted] [redacted]
- [redacted] [redacted]
- [redacted] [redacted]
- [redacted] [redacted]
- [redacted] [redacted]

[redacted]
[redacted]
[redacted]
[redacted]

[redacted]
[redacted]

[redacted]
[redacted]
[redacted]

409 Safety endpoints will be analyzed descriptively based on the SAF, and subjects will be
410 summarized based on the actual treatment they received.

411 **4.5 Protocol Deviations**

412 All protocol deviations (PD) will be tracked throughout the study and classified by deviation
413 type, either minor or major. Protocol deviations represent a failure to adhere to the clinical
414 study protocol. The two types of deviations are defined as:

- 415 • Minor protocol deviation is any change, divergence, or departure from the study
416 design or procedures of a research protocol that has not been approved by the IRB and
417 which does not have a major impact on the subject's rights, safety or well-being, or
418 the completeness, accuracy and reliability of the study data.
- 419 • Major protocol deviation is any change, divergence, or departure from the study
420 design or procedures of a research protocol that has not been approved by the IRB and
421 which has a major impact on the subject's rights, safety or well-being, or the
422 completeness, accuracy and reliability of the study data. [REDACTED]

- [REDACTED] [REDACTED] [REDACTED]
- [REDACTED] [REDACTED] [REDACTED]
- [REDACTED] [REDACTED] [REDACTED]
- [REDACTED] [REDACTED] [REDACTED]
- [REDACTED] [REDACTED] [REDACTED]
- [REDACTED] [REDACTED] [REDACTED]

430 Prior to interim database freeze and final database lock, each deviation will be reviewed to
431 determine if it excludes the patient from any of the analysis sets or any particular planned
432 analysis. These determinations will then be described in the relevant clinical study report.
433 [REDACTED]

434 Minor protocol deviations will be presented as well. All deviations will be retained within
435 the deviations tracker (considered the source document).

436 Protocol deviations attributable to the COVID-19 pandemic regardless whether deemed
437 major or minor will be provided in a separate listing if deemed necessary. Protocol
438 deviations will be presented in summary tables, for IA and overall, respectively.

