[REDACTED]

[REDACTED]

848 Non-TEAEs will be listed only and will not be included for analysis and summarization.

849 All AEs will be presented in a by-treatment and by-subject listing, detailing the verbatim
850 term, SOC, PT, application site reaction or not, related to study indication or not, start date,
851 stop date, time since most recent dose of IP, severity, outcome, relationship to study drug,
852 action taken regarding study drug, action taken to treat AE, seriousness and criteria for
853 seriousness. Serious AEs (SAEs) and TEAEs leading to study medication discontinuation,
854 AEs of Special Interest (AESI), and events of clinical interest (ECI) will also be presented in
855 separate listings.

856 An AE profile for the Safety Analysis Set will be provided for Part 1, Parts 2 and 3, and
857 overall, which summarizes the subject incidence, by treatment received for the following
858 information:

- 859 • Any TEAEs;
- 860 • Non-TEAEs;
- 861 • Drug-related TEAEs;
- 862 • Any TEAEs with an outcome of death;
- 863 • Treatment-emergent SAEs;
- 864 • Drug-related treatment-emergent SAEs;
- 865 • TEAEs leading to discontinuation of study medication;
- 866 • Drug-related TEAEs leading to discontinuation of study medication;

- 867 • Any AEs of special interest, including:
868 ○ Injection site reactions
869 ○ Severe infections
870 ○ Malignancies (excluding carcinoma in situ of the cervix).
871 ○ Non-melanoma skin cancer
872 ○ Melanoma skin cancer
873 ○ Major Adverse Cardiovascular Events (MACE)
874 ○ Study treatment-related hypersensitivity reactions.

[REDACTED]

[REDACTED]

891 The number and percentage of subjects with TEAEs will be summarized for each treatment
892 arm and/or in total by SOC and PT. Drug-related TEAEs, TEAEs leading to discontinuation
893 of study drug, drug-related TEAEs leading to discontinuation of study drug, treatment-
894 emergent SAEs, and drug-related treatment-emergent SAEs will be summarized in the same
895 manner. For these summaries, subjects with multiple AEs will be counted only once per SOC
896 and PT.

897 TEAEs by maximum severity and TEAEs by relationship to study treatment, and commonly
898 occurring TEAEs, i.e., those that occur in [REDACTED] of the subjects in either treatment arm,
899 will be summarized by SOC and PT by treatment received in Part 1, Parts 2 and 3, and
900 overall.

901 Injection site reactions will be described in a by-subject listing and may be summarized
902 separately if deemed necessary.

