1049 severe scalp psoriasis and so the analysis is moved to the ‘Other Secondary’ section.

1050 [REDACTED]
[REDACTED]
[REDACTED]
[REDACTED]

[REDACTED]

1073 Sensitivity analyses are revised to include only primary and key secondary endpoints,
1074 since other secondary efficacy endpoints are less meaningful to the objectives of the
1075 study.

1076 Section 4.11 defines examinations of subgroups and sensitivity analyses.

1077 Multiple sections identify removal of sensitivity analyses related to secondary
1078 endpoints. Section 3 defines dose-relative criteria for completion of Part 1 and
1079 initiation of Parts 2 and 3 of the protocol.

1080 Handling of COVID-19 pandemic-related events are specified in the SAP in the
1081 sections shown below:

- 1082 ○ 4.3 Disposition of Subjects,
- 1083 ○ 4.5 Protocol Deviations,
- 1084 ○ 4.8 Study Drug Exposure and Compliance,

- 1085 ○ 4.9.1 Primary Estimand and Intercurrent Events,
- 1086 ○ 4.12 COVID-19 Pandemic Impacted Subject Assessments
- 1087 Section 4.9.6 describes by-subject displays
- 1088 Section 6.2.1 describes COVID-19 impacts to Visits
- 1089 Section 6.2.4 describes SAS[®] Procedures for M-N methodology implementation

[REDACTED]	[REDACTED]
[REDACTED]	[REDACTED]
[REDACTED]	[REDACTED]
[REDACTED]	[REDACTED]
[REDACTED]	[REDACTED]
[REDACTED]	[REDACTED]

1105 **6 PROGRAMMING CONSIDERATIONS**

1106 All tables, data listings, figures (TLFs), and statistical analyses will be generated using SAS®
1107 Version 9.4 or above. Generated outputs will adhere to the following specifications.

1108 **6.1 Table, Listing, and Figure Format**

1109 **6.1.1 General**

- 1110 1) All TLFs will be produced in landscape format.
1111 2) All TLFs will be produced using the Courier New font, size 8.
1112 3) The data displays for all TLFs will have a 1.5-inch binding margin on top of a
1113 landscape oriented page and a minimum 1-inch margin on the other 3 sides.
1114 4) Headers and footers for figures will be in Courier New font, size 8.
1115 5) Legends will be used for all figures with more than 1 variable, group, or item
1116 displayed.
1117 6) TLFs will be in black and white (no color).
1118 7) Specialized text styles, such as bolding, italics, borders, shading, and superscripted
1119 and subscripted text, will not be used in the TLFs. On some occasions, superscripts 1,
1120 2, or 3 may be used (see below).
1121 8) Only standard keyboard characters will be used in the TLFs. Special characters, such

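### The SAP's date boundary leaves the day of the placebo arm's first tildrakizumab injection in Part 1, so same-day adverse events mapped by onset date fall in the placebo-controlled period

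*SAP*

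**What the plan says.** SAP Section 3 defines the study Parts by calendar date. Part 1 takes efficacy and safety assessments "before or on the date of injection at Week 16", with redacted text following. Part 2 takes "All assessments of efficacy and safety after the date of injection at Week 16 and before or" on the Week 52 injection date; its lower limit is not interrupted by any redaction. The same paragraph makes the switch: "At Week 16, subjects initially randomized to placebo will be switched over to receive" tildrakizumab 100 mg. SAP 4.13 describes these boundaries this way: "Section 3 defines dose-relative criteria for completion of Part 1 and" the start of Parts 2 and 3.

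The Parts then structure the AE output. SAP 4.10.1 states "An AE profile for the Safety Analysis Set will be provided for Part 1, Parts 2 and 3, and" overall. It adds that events by maximum severity, events by relationship and commonly occurring events "will be summarized by SOC and PT by treatment received in Part 1, Parts 2 and 3, and" overall. The profile includes injection site reactions and treatment-related hypersensitivity. Under SAP 4.4, subjects in the safety analyses are "summarized based on the actual treatment they received".

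The protocol synopsis (Overall Design) counts AE monitoring among the safety assessments: "Safety assessments including adverse event (AE)/serious adverse event (SAE) monitoring". Protocol 8.3 lists a date of onset among the items for each AE entry and no clock time.

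**The concern.** A date boundary works for the Week 16 efficacy scores and other assessments made before the injection that day. It does not work for an event that the injection itself provokes. For a placebo-arm subject, the Week 16 injection is the first exposure to tildrakizumab, and an injection site or hypersensitivity reaction can begin within hours. Under the visible rule, applied to onset date, that reaction belongs to Part 1.

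Two tables would then mislead. The Part 1 table, which is the only randomized comparison with placebo, could include reactions to active drug in subjects randomized to placebo. The Parts 2 and 3 tables, where a reader would look for first-dose reactions in the switched subjects, would lack those that started on the day of dosing. Injection site reactions and treatment-related hypersensitivity are both listed as primary safety endpoints in protocol Table 1, so their placement should not be left to the programmer.

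**Working it through.** No figure in the plan is in dispute, so there is nothing to reproduce. The check has two parts: apply the rule, then size the effect.

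**Applying the rule.** Let d be the AE onset date minus the Week 16 injection date, in days. Section 3 gives Part 1 if d ≤ 0 and Part 2 if d > 0:

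- d = −1: Part 1
- d = 0: Part 1
- d = +1: Part 2

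An event with d = 0 falls in Part 1 whether it began before or after the injection.

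**Looking for another rule in the visible text.**

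- The treatment-emergent definition (SAP 4.10.1) is anchored to the first administration of any study treatment, placebo included. It does not restart at the switch.
- The counting rules in SAP 6.2.3 decide whether an event is treatment-emergent, not which Part it belongs to.
- Treatment received sets the table column, not the Part. By the end of the switch day these subjects have received both treatments, and no visible rule says which applies.
- SAP 4.10 identifies the switched subjects as a group for reporting at the end of the study, after the Week 16 results have been reported.
- The AE listing shows time since the most recent dose, but no visible text uses it to assign a Part.

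**Sizing.** The placebo arm has n = 107 planned subjects (SAP Section 3). The same-day reaction rate p is not in the documents, so 0.5%, 1% and 2% are assumed. Dropout before Week 16 is assumed to be 0% or 10% (107 × 0.9 = 96.3, taken as 96 for the probabilities).

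One affected subject with no earlier event of that type, counted as placebo: 1/107 = 0.93 percentage points.

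Expected cases = n × p, and P(at least one) = 1 − (1 − p)^n:

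| p | Expected, n = 107 | P(≥1), n = 107 | Expected, n = 96.3 | P(≥1), n = 96 |
|---|---|---|---|---|
| 0.5% | 0.54 | 41.5% | 0.48 | 38.2% |
| 1% | 1.07 | 65.9% | 0.96 | 61.9% |
| 2% | 2.14 | 88.5% | 1.93 | 85.6% |

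**Between-arm difference in Part 1.** Assume true Part 1 rates r of 5% (tildrakizumab) and 2% (placebo), and the same independent same-day risk p in both arms. The reported rate is r + p(1 − r):

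- p = 1%: 5% + 1% × 0.95 = 5.95%; 2% + 1% × 0.98 = 2.98%; difference 2.97 points.
- p = 2%: 5% + 2% × 0.95 = 6.90%; 2% + 2% × 0.98 = 3.96%; difference 2.94 points.

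The difference without same-day events is 3.00 points. On the equal-risk assumption it hardly moves; what changes is the placebo arm's own incidence.

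**The case against.** The strongest objection is that the mapping key is assumed. Section 3 sorts assessments, and no visible sentence says that AEs go to Parts by onset date. A reaction that begins in the evening and is collected at the next visit could be read as assessed after the injection date, and so as Part 2. Text is also redacted immediately after the Part 1 boundary and in two stretches of SAP 4.10.1. Either place could hold a qualifier or an AE-specific rule, and describing the criteria as dose-relative suggests that dosing was considered. These points stand. They make the finding conditional and put a check of the unredacted SAP first. They do not remove it: onset date is the only event timing visible in protocol 8.3, and the start of Part 2 is unredacted.

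The second objection is that safety is tabulated by treatment received, so an active-drug reaction should not appear under placebo. That may be the intention, and for this reason the 0.93-point figure is given only for the case where the event is counted as placebo. The column does not settle the Part, however: the event would still be missing from the Parts 2 and 3 tables.

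Third, the assumed rates are illustrative, and a chance of one case is not a chance of a changed conclusion. This is right, and it limits the severity. Finally, any date-level convention misplaces some same-day events. This is also right; the choice is about which errors to accept and whether the convention is written down.

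**Conclusion.** The concern holds as a minor point. On the visible text, if AEs are assigned to Parts by onset date, a reaction to the placebo arm's first tildrakizumab injection that starts the same day is tabulated in the placebo-controlled period. No visible rule prevents this.

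The consequence is confined to descriptive by-Part safety tables. Treatment-emergent status, overall counts, listings, efficacy, alpha and sample size are unaffected. At the assumed rates, about one or two subjects might be involved. Confidence is medium, because redacted text could already contain the missing rule.

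**What to change.** First confirm in the unredacted SAP whether AEs starting on the day of the Week 16 injection are already covered. If they are, nothing more is needed.

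If not, keep the Section 3 date rule for efficacy and other pre-dose assessments and add to SAP 4.10.1: AEs are assigned to Parts by onset; an AE starting on the Week 16 injection date belongs to Part 2 unless the record shows that it began before the injection; and treatment received for such an event in a switched subject is tildrakizumab.

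The cost is one or two sentences and a programming flag. The planned listing of time since the most recent dose will help find the cases. Since the visible AE entry list gives only a date of onset, a before-or-after-injection indicator may be needed for that visit. The drawback is that events of unknown time that in fact began before the injection on that day would move to Part 2.
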